5.1.5.3 Dose Modification

Adverse events (both non-serious and serious) associated with pembrolizumab exposure may represent an immunologic etiology. These adverse events may occur shortly after the first dose or several months after the last dose of treatment. MK-3475 will be withheld for MK-3475-related toxicities and severe or life-threatening AEs as per Table 5. See Section 5.6.1 and Events of Clinical Interest Guidance Document for supportive care, including use of corticosteroids.

Table 5: Dose modification guidelines for MK-3475 related adverse events.

Toxicity	Hold Treatment For Grade	Timing for Restarting Treatment	Treatment Discontinuation
Diarrhea/Colitis	2-3	Toxicity resolves to Grade 0-1	Toxicity does not resolve within 12 weeks of last dose or inability to reduce corticosteroid to 10 mg or less of prednisone or equivalent per day within 12 weeks
	4	Permanently discontinue	Permanently discontinue
AST, ALT, or Increased Bilirubin	2	Toxicity resolves to Grade 0-1	Toxicity does not resolve within 12 weeks of last dose
	3-4	Permanently discontinue (see exception below) ^a	Permanently discontinue
Type 1 diabetes mellitus (if new onset) or Hyperglycemia	T1DM or 3-4	Hold pembrolizumab for new onset Type 1 diabetes mellitus or Grade 3-4 hyperglycemia associated with evidence of beta cell failure	Resume pembrolizumab when patients are clinically and metabolically stable
Hypophysitis	2-4	Toxicity resolves to Grade 0-1. Therapy with pembrolizumab can be continued while endocrine replacement therapy is instituted	Toxicity does not resolve within 12 weeks of last dose or inability to reduce corticosteroid to 10 mg or less of prednisone or equivalent per day within 12 weeks
Hyperthyroidism	3	Toxicity resolves to Grade 0-1	Toxicity does not resolve within 12 weeks of last dose or inability to reduce corticosteroid to 10 mg or less of prednisone or equivalent per day within 12 weeks
	4	Permanently discontinue	Permanently discontinue
Hypothyroidism		Therapy with pembrolizumab	Therapy with pembrolizumab can be continued

Toxicity	Hold Treatment For Grade	Timing for Restarting Treatment	Treatment Discontinuation
Infusion Reaction		can be continued while thyroid replacement therapy is instituted	while thyroid replacement therapy is instituted
	2 ^b	Toxicity resolves to Grade 0-1	Permanently discontinue if toxicity develops despite adequate premedication
	3-4	Permanently discontinue	Permanently discontinue

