Pneumonitis	2	Toxicity resolves to Grade 0-1	Toxicity does not resolve within 12 weeks of last dose or inability to reduce corticosteroid to 10 mg or less of prednisone or equivalent per day within 12 weeks
	3-4	Permanently discontinue	Permanently discontinue
Renal Failure or Nephritis	2	Toxicity resolves to Grade 0-1	Toxicity does not resolve within 12 weeks of last dose or inability to reduce corticosteroid to 10 mg or less of prednisone or equivalent per day within 12 weeks
	3-4	Permanently discontinue	Permanently discontinue
All Other Drug-Related Toxicity ^c	3 or Severe	Toxicity resolves to Grade 0-1	Toxicity does not resolve within 12 weeks of last dose or inability to reduce corticosteroid to 10 mg or less of prednisone or equivalent per day within 12 weeks
	4	Permanently discontinue	Permanently discontinue

Note: Permanently discontinue for any severe or Grade 3 drug-related AE that recurs or any life-threatening event.

^a For patients with liver metastasis who begin treatment with Grade 2 AST or ALT, if AST or ALT increases by greater than or equal to 50% relative to baseline and lasts for at least 1 week then patients should be discontinued.

^b If symptoms resolve within one hour of stopping drug infusion, the infusion may be restarted at 50% of the original infusion rate (e.g., from 100 mL/hr to 50 mL/hr). Otherwise dosing will be held until symptoms resolve and the subject should be premedicated for the next scheduled dose; Refer to Infusion Treatment Guidelines for further management details.

^c Patients with intolerable or persistent Grade 2 drug-related AE may hold study medication at physician discretion. Permanently discontinue study drug for persistent Grade 2 adverse reactions for which treatment with study drug has been held, that do not recover to Grade 0-1 within 12 weeks of the last dose.

Dosing interruptions are permitted in the case of medical / surgical events or logistical reasons not related to study therapy (e.g., elective surgery, unrelated medical events, patient vacation, and/or holidays). Subjects should be placed back on study therapy within 3 weeks of the scheduled interruption, unless otherwise discussed with the Sponsor. The reason for interruption should be documented in the patient's study record.

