12.8 Evaluating Adverse Events

An investigator who is a qualified physician, will evaluate all adverse events as to:

V4.0 Grading	CTCAE	Grade 1	Mild; asymptomatic or mild symptoms; clinical or diagnostic observations only; intervention not indicated.
		Grade 2	Moderate; minimal, local or noninvasive intervention indicated; limiting age-appropriate instrumental ADL.
		Grade 3	Severe or medically significant but not immediately life-threatening; hospitalization or prolongation of hospitalization indicated; disabling; limiting self-care ADL.
		Grade 4	Life threatening consequences; urgent intervention indicated.
		Grade 5	Death related to AE
Seriousness	A serious adverse event is any adverse event occurring at any dose or during any use of Merck product that:		
	†Results in death; or		
	†Is life threatening; or places the subject, in the view of the investigator, at immediate risk of death from the event as it occurred (Note: This does not include an adverse event that, had it occurred in a more severe form, might have caused death.); or		
	†Results in a persistent or significant disability/incapacity (substantial disruption of one's ability to conduct normal life functions); or		
	†Results in or prolongs an existing inpatient hospitalization (hospitalization is defined as an inpatient admission, regardless of length of stay, even if the hospitalization is a precautionary measure for continued observation. (Note: Hospitalization [including hospitalization for an elective procedure] for a preexisting condition which has not worsened does not constitute a serious adverse event.); or		
	†Is a congenital anomaly/birth defect (in offspring of subject taking the product regardless of time to diagnosis); or		
	Is a new cancer; (that is not a condition of the study) or		
	(For Merck Only. BIPI does not list criteria for overdose) Is an overdose (whether accidental or intentional). Any adverse event associated with an overdose is considered a serious adverse event. An overdose that is not associated with an adverse event is considered a non-serious event of clinical interest and must be reported		
	Other important medical events that may not result in death, not be life threatening, or not require hospitalization may be considered a serious adverse event when, based upon appropriate medical judgment, the event may jeopardize the subject and may require medical or surgical intervention to prevent one of the outcomes listed previously (designated above by a †).		

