3.3 Endocrine

The following AE terms, if considered \geq Grade 3 or if \geq Grade 2 and require holding/discontinuation/ modification of pembrolizumab dosing, are considered ECIs and should be reported to the Sponsor within 24 hours of the event:

- Adrenal insufficiency
- Hyperthyroidism
- Hypophysitis
- Hypopituitarism
- Hypothyroidism
- Thyroid disorder
- Thyroiditis

All attempts should be made to rule out other causes such as brain metastases, sepsis and/or infection. However the AE should be reported regardless of etiology.

Hypophysitis or other symptomatic endocrinopathy other than hypo- or hyperthyroidism

Grade 2-4 events:

- Report as ECI if appropriate
- Hold pembrolizumab
- Rule out infection and sepsis with appropriate cultures and imaging.
- Monitor thyroid function or other hormonal level tests and serum chemistries more frequently until returned to baseline values.
- Pituitary gland imaging should be considered (MRIs with gadolinium and selective cuts of the pituitary can show enlargement or heterogeneity and confirm the diagnosis).
- Treat with prednisone 40 mg p.o. or equivalent per day. When symptoms improve to Grade 1 or less, steroid taper should be started and continued over no less than 4 weeks. Replacement of appropriate hormones may be required as the steroid dose is tapered.
- Permanently discontinue for inability to reduce corticosteroid dose to 10 mg or less of prednisone or equivalent per day within 12 weeks.
- Hypophysitis with clinically significant adrenal insufficiency and hypotension, dehydration, and electrolyte abnormalities (such as hyponatremia and hyperkalemia) constitutes adrenal crisis.
- Consultation with an endocrinologist may be considered.

Hyperthyroidism and Hypothyroidism

Thyroid disorders can occur at any time during treatment. Monitor patients for changes in thyroid function (at the start of treatment, periodically during treatment, and as indicated based on clinical evaluation) and for clinical signs and symptoms of thyroid disorders.

Grade 2 hyperthyroidism, Grade 2-4 hypothyroidism events:

- Report as ECI if appropriate (see Table 1)
- Monitor thyroid function or other hormonal level tests and serum chemistries more frequently until returned to baseline values.
- Thyroid hormone and/or steroid replacement therapy to manage adrenal insufficiency.
- Therapy with pembrolizumab can be continued while treatment for the thyroid disorder is instituted.

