- Hold pembrolizumab for new onset Type 1 diabetes mellitus or Grade 3-4 hyperglycemia associated with evidence of beta cell failure, and resume pembrolizumab when patients are clinically and metabolically stable.
- Insulin replacement therapy is recommended for Type I diabetes mellitus and for Grade 3-4 hyperglycemia associated with metabolic acidosis or ketonuria.
- Evaluate patients with serum glucose and a metabolic panel, urine ketones, glycosylated hemoglobin, and C-peptide.
- Consultation with an Endocrinologist is recommended.
- Consider local testing for islet cell antibodies and antibodies to GAD, IA-2, ZnT8, and insulin may be obtained.

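### Table 5's Note conflicts with three endocrine rows at Grade 4, and Table 5 permits MK-3475 restart in two situations where the appended guidance says stop permanently

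*Combined protocol and SAP*

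**What the plan says.** Section 5.1.5.3 sends MK-3475 dose modification to Table 5 and cites Section 5.6.1 and the appended guidance (12.9) for supportive care. The Note under Table 5 reads: "Permanently discontinue for any severe or Grade 3 drug-related AE that recurs or any life-threatening event". Section 12.8 describes Grade 4 as "Life threatening consequences; urgent intervention indicated".

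Three endocrine rows of Table 5 point the other way:

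- Hypophysitis, Grades 2-4: restart on recovery to Grade 0-1, and "Therapy with pembrolizumab can be continued while endocrine replacement therapy is instituted".
- Type 1 diabetes or hyperglycemia, Grades 3-4: "Hold pembrolizumab for new onset Type 1 diabetes mellitus or Grade 3-4 hyperglycemia associated with evidence of beta cell failure", followed in the discontinuation column by "Resume pembrolizumab when patients are clinically and metabolically stable".
- Hypothyroidism: treatment may continue during thyroid replacement, with no grade stated.

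Table 5 has no neurologic row, and Section 5.6.1 has no neurologic entry. Its Grade 2 pneumonitis row allows restart at Grade 0-1 and does not separate a first from a second episode.

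**The concern.** A patient with Grade 4 hypophysitis, or with Grade 4 hyperglycemia and beta cell failure, meets both a rule to stop MK-3475 for good and a rule that lets it resume. One site may follow the Note and another the row. In a trial whose primary objective is safety and tolerability, stopping rules should be applied alike at all centers.

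The second issue is re-exposure. A patient who recovers from a first Grade 3 Guillain-Barré or myasthenic syndrome, or from a second Grade 2 pneumonitis, may be re-dosed under Table 5. The guidance appended to the same protocol says such a patient should not receive the drug again.

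**Working it through.** No arithmetic applies beyond counting, so the texts are set side by side.

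**Step 1. The Note against the rows of Table 5 at Grade 4.** Table 5 has ten toxicity rows. Seven require a permanent stop at Grade 4: diarrhea/colitis, hepatic, hyperthyroidism, infusion reaction, pneumonitis, renal, and the catch-all for other drug-related toxicity. The remaining 10 − 7 = 3 do not.

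| Event at Grade 4 | Table 5 row | Table 5 Note | Guidance 3.3 |
|---|---|---|---|
| Hypophysitis | Restart at Grade 0-1, or continue with replacement | Permanent stop | Hold; permanent stop only if steroids cannot be reduced |
| T1DM/hyperglycemia | Hold, then resume when stable | Permanent stop | Hold, then resume when stable |
| Hypothyroidism | Continue with replacement | Permanent stop | Continue (Grades 2-4) |

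For hypophysitis, guidance 3.3 works under the heading "Hypophysitis or other symptomatic endocrinopathy other than hypo- or hyperthyroidism", covers Grades 2-4 together, and gives one condition for ending treatment: "Permanently discontinue for inability to reduce corticosteroid dose to 10 mg or less of prednisone or equivalent per day within 12 weeks". For diabetes and hyperglycemia it says "resume pembrolizumab when patients are clinically and metabolically stable". The guidance therefore agrees with all three rows, and the Note is the outlier. The Note has no exception clause, although the hepatic row shows that the table flags exceptions when it wants them.

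**Step 2. Which text governs.** Section 5.1.5.3 assigns dose modification to Table 5. The guidance overview (12.9, Section 1) defers to the protocol's own wording on dose modification. Table 5 therefore prevails where the two differ.

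**Step 3. Table 5 against the guidance on re-dosing.**

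| Situation | Table 5 (governing) | Guidance |
|---|---|---|
| First Grade 3 neurologic immune event | Catch-all row: restart at Grade 0-1 if, within 12 weeks, it resolves and steroids are down to 10 mg or less | 3.6: discontinue |
| Grade 4 neurologic immune event | Permanent stop | 3.6: discontinue (agrees) |
| Second Grade 2 pneumonitis | Grade 2 row: restart permitted, same 12-week limits, no episode limit | 3.1: discontinue |

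The guidance overview defines discontinue as permanent. Guidance 3.6 names four terms: autoimmune neuropathy, demyelinating polyneuropathy, Guillain-Barré syndrome and myasthenic syndrome. The Note's recurrence clause does not reach a second Grade 2 pneumonitis, because it covers only severe or Grade 3 events.

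**Step 4. Effect on dose finding.** The DLT definition (Section 5.3) covers Cycle 1 toxicity and does not depend on whether MK-3475 is later resumed. The de-escalation rule (Section 5.1.5.2) counts DLTs. Neither uses the conflicting entries.

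**The case against.** **Precedence is settled.** A reader might infer that a site facing a Grade 3 neurologic event has two competing instructions of equal rank. The documents do not support that, as Step 2 shows. The overview's remark about individual clinical judgment explains why the management advice is a guideline; it does not undo the deference to the protocol. This part of the objection stands, but its consequence is that the looser rule is the operative one.

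**Restart is narrowly gated.** Table 5 permits restart without requiring it, the 12-week limits apply, and the Note ends treatment if a Grade 3 event recurs. Section 12.8 requires advance approval of rechallenge after a serious event that the drug may have caused. These limits are real and reduce the risk. However, the approval is to follow the protocol's dose modification guidelines, which leads back to Table 5. Section 5.8 lets the investigator withdraw a subject, but its criterion for unacceptable adverse experiences points to a Section 5.2.1.2 that the protocol does not contain.

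**Life-threatening need not mean every Grade 4.** Section 12.8 also defines life-threatening as a seriousness criterion (immediate risk of death), so the Note could be an override for only the gravest cases. That would narrow the conflict without removing it: the three rows make no carve-out for those cases either.

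**Specific rows qualify a general note.** This is a sensible reading, and guidance 3.3 suggests that it was the intent. The protocol does not state such a rule, and the Note says any.

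**Conclusion.** The point holds as a limited safety inconsistency that should be corrected. Three Table 5 rows conflict with the Note at Grade 4. In two further situations (a first Grade 3 event among four named neurologic terms, and a second Grade 2 pneumonitis) the governing table permits re-dosing where the appended guidance says stop permanently.

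The first part rests on reading life-threatening as Grade 4, which the grading table in Section 12.8 supports. The second rests on Table 5 taking precedence, which Section 5.1.5.3 and the guidance overview support. The planned maximum is 38 patients, and only those with these events are affected; without event rates no count can be given.

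Two stronger readings go too far. A reader might infer that Table 5 is always the looser text. It is not: Grade 4 adrenal insufficiency is a permanent stop under the catch-all row but a hold under guidance 3.3. A reader might also infer that dose finding is compromised, but the DLT and MTD rules are unaffected.

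**What to change.** Amend Table 5 in three places:

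1. Reword the end of the Note to: *any life-threatening event, except hypophysitis, hypothyroidism and T1DM/hyperglycemia managed as specified in the rows above*. This matches guidance 3.3 for those three events and leaves the Grade 4 stop for adrenal insufficiency in place.
2. Add a row: *Neurologic immune-related events, Grade 3-4: permanently discontinue*.
3. Add to the pneumonitis row: *second episode of Grade 2 or higher: permanently discontinue*.

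The cost is a protocol amendment to one table and its Note, with no added patients, visits or tests. Change 1 has a downside: it confirms that MK-3475 may be given after a controlled Grade 4 endocrine event, which the Note now bars. A sponsor that prefers the stricter rule could instead write a Grade 4 permanent stop into the three rows, at the price of departing from guidance 3.3. Changes 2 and 3 would stop MK-3475 in a few patients who might otherwise have resumed.

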5.1.6 Timing of Dose Administration

Trial treatment should be administered on Day 1 of each cycle after all procedures/assessments have been completed as detailed on the Trial Flow Chart (Section 6.0). Trial treatment may be administered up to 3 days before or after the scheduled Day 1 of each cycle due to administrative reasons.

All trial treatments may be administered on an outpatient basis.

MK-3475 200 mg will be administered as a 30 minute IV infusion every 3 weeks. Sites should make every effort to target infusion timing to be as close to 30 minutes as possible. However, given the variability of infusion pumps, a window of -5 minutes and +10 minutes is permitted (i.e., infusion time is 30 minutes: -5 min/+10 min).

Afatinib is an oral agent that will be given once daily for 21 days per cycle starting on day 1 of each cycle before administration of MK-3475. It should be taken in the morning with 200 mL of water.

The medication should be taken at the same time each day (\pm 2 hours) without food (at least one hour before or at least 2 hours after a meal).

Missed doses of afatinib can be made up during the same day. Otherwise, the dose must be skipped and patients should take the next scheduled dose at the usual time. Patients with emesis must not take a replacement dose. A missed dose of afatinib should not be taken within 12 hours of the next dose.

5.1.7 Trial Blinding/Masking

This is an open-label trial; therefore, the Sponsor-Investigator and subject will know the treatment administered.

5.2 Treatment Allocation

Patients will be enrolled into the dose de-escalation protocol until the MTD is reached. Then patients will be enrolled into 2 cohorts for the dose expansion at the recommended expansion dose and RP2D. Cohort (Arm) A: will be concurrent MK-3475 + afatinib at initiation of treatment and Cohort (Arm) B: will be lead in MK-3475 for 2 cycles followed by concurrent MK-3475 and afatinib. The recommended dose for the dose expansion cohorts and RP2D dose will be informed by the MTD determined in the de-dose escalation phase and assessment of the overall toxicity at the treated dose levels.

After the expansion dose (MTD) is determined, for the expansion phase we will enroll and complete Cohort A: Afatinib + MK-3475 (Concurrent) to further define toxicities at the MTD in the dose expansion. After completion of Cohort A, we will enroll patients into Cohort B (lead-in MK-3475 followed by combination afatinib and MK-3475 commencing at cycle #3).

5.3 Definition of Dose Limiting Toxicities (DLT)

All toxicities will be graded using National Cancer Institute (NCI) CTCAE Version 4.0. The occurrence of any of the following toxicities during Cycle 1 will be considered a DLT, if judged by the Investigator to be possibly, probably or definitely related to study drug (either afatinib or MK-3475) administration:

1. Grade 4 non-hematologic toxicity (not laboratory).
2. Grade 4 hematologic toxicity lasting ≥ 14 days.
3. Grade 3 non-hematologic toxicity (not laboratory) lasting > 3 days despite optimal supportive care with maximal supportive care for diarrhea and rash. See description of maximal supportive care for diarrhea and rash attributed to afatinib below.
4. Any Grade 3 or Grade 4 non-hematologic laboratory value if:
 - Medical intervention is required to treat the patient, or
 - The abnormality leads to hospitalization, or
 - The abnormality persists as \geq grade 3 for > 1 week.
5. Febrile neutropenia Grade 3 or Grade 4:
 - Grade 3 is defined as ANC $< 1000/\text{mm}^3$ with a single temperature of > 38.3 degrees C (101 degrees F) or a sustained temperature of ≥ 38 degrees C (100.4 degrees F) for more than one hour
 - Grade 4 is defined as ANC $< 1000/\text{mm}^3$ with a single temperature of > 38.3 degrees C (101 degrees F) or a sustained temperature of ≥ 38 degrees C (100.4 degrees F) for more than one hour, with life-threatening consequences and urgent intervention indicated.
6. Thrombocytopenia $< 25,000/\text{mm}^3$ if associated with:
 - A bleeding event which does not result in hemodynamic instability but requires an elective platelet transfusion, or
 - A life-threatening bleeding event which results in urgent intervention and admission to an Intensive Care Unit
 - Grade 5 toxicity (i.e. death).
7. Diarrhea is an expected adverse event from afatinib. Diarrhea attributed to afatinib will be considered a DLT if grade 3 despite maximal medical management for > 72 hours. Maximal medical management will be defined as anti-diarrheal management that includes: loperamide, diphenoxylate and atropine, and tincture of opium. Grade 4 diarrhea will be considered a DLT.

8. Acneiform rash is an expected adverse event from afatinib. Acneiform rash attributed to afatinib will be considered a DLT if grade 3 despite maximal medical management for > 72 hours. Maximal medical management will be defined as oral antibiotic, preferably doxycycline, cleocin solution or cream and topical steroids. In addition an asymptomatic/minimally symptomatic classic acneiform rash will only be considered a DLT if it covers \geq 50% BSA. Grade 4 rash will be considered a DLT.
9. To be evaluable for a DLT, 80% of dose must have been administered in cycle 1 unless a DLT occurred.
10. Delay in starting cycle 2 of \geq 14 days due to toxicity related to afatinib and/or MK-3475

